4.3. Exclusion Criteria

Subjects who meet any of the following exclusion criteria are not to be enrolled in this study:

- 1) Pregnant women, women who are breastfeeding or who believe they may wish to become pregnant during the course of the study
- 2) Males and females of reproductive potential who are unwilling to use an "effective", protocol-specified method(s) of contraception during the study. For a list of protocol-specified Contraceptive methods, refer to Appendix 5.

- 3) Co-infection with HCV, HIV, or HDV
 - Subjects who are HCV positive, but have a documented negative HCV RNA, are eligible
- 4) Evidence of hepatocellular carcinoma (e.g. as evidenced by recent imaging)
- 5) Current evidence of, or recent (\leq 5 years) history of clinical hepatic decompensation (e.g., ascites, encephalopathy or variceal hemorrhage)
- 6) Abnormal hematological and biochemical parameters, including:
 - a) Hemoglobin < 10 g/dL
 - b) Absolute neutrophil count < 750/mm³
 - c) Platelets $\leq 50,000/\text{mm}^3$
 - d) AST or ALT $> 5 \times ULN$
 - e) Albumin < 3.0 mg/dL
 - f) INR $> 1.5 \times$ ULN (unless stable on anticoagulant regimen)
 - g) Total bilirubin $> 2.5 \times ULN$
- 7) Received solid organ or bone marrow transplant
- 8) Significant renal, cardiovascular, pulmonary, or neurological disease in the opinion of the investigator
- 9) Malignancy within 5 years prior to Screening, with the exception of specific cancers that are cured by surgical resection (e.g. basal cell skin cancer, etc.). Subjects under evaluation for possible malignancy are not eligible.
- 10) Currently receiving therapy with immunomodulators (e.g. corticosteroids), nephrotoxic agents, or agents capable of modifying renal excretion
- 11) Known hypersensitivity to study drugs, metabolites, or formulation excipients
- 12) Current alcohol or substance abuse judged by the investigator to potentially interfere with subject compliance
- 13) Any other clinical condition or prior therapy that, in the opinion of the Investigator, would make the subject unsuitable for the study or unable to comply with dosing requirements.
- 14) Use of investigational agents within 3 months of screening, unless allowed by the Sponsor
- 15) Use of any prohibited medications as described in Section 5.4. Subjects on prohibited medications who are otherwise eligible will need a wash out period of at least 30 days prior to the Baseline visit

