- 5) Estimated creatinine clearance ≥ 50 ml/min (using the Cockcroft-Gault method) based on serum creatinine and actual body weight as measured at the Screening evaluation, as follows:

(140 – age in years) (body weight [kg]) (72) (serum creatinine [mg/dL])

(Note: multiply estimated rate by 0.85 for women)

- 6) Normal ECG (or if abnormal, determined by the Investigator not to be clinically significant)
- 7) Must be willing and able to comply with all study requirements

Exclusion Criteria

Subjects who meet any of the following exclusion criteria are not to be enrolled in this study:

- Pregnant women, women who are breastfeeding or who believe they may wish to become pregnant during the course of the study
- 2) Males and females of reproductive potential who are unwilling to use an "effective", protocol-specified method(s) of contraception during the study. For a list of protocol-specified Contraceptive methods, refer to Appendix 5.
- 3) Co-infection with HCV, HDV, HIV
 - Subjects who are HCV positive, but have a documented negative HCV RNA, are eligible
- 4) Evidence of hepatocellular carcinoma (e.g. as evidenced by recent imaging)
- 5) Current evidence of, or recent (≤ 5 year) history of clinical hepatic decompensation (e.g., ascites, encephalopathy or variceal hemorrhage)
- 6) Abnormal hematological and biochemical parameters, including:
 - a) Hemoglobin < 10 g/dL
 - b) Absolute neutrophil count < 750/mm³
 - c) Platelets $< 50.000/\text{mm}^3$
 - d) AST or ALT $> 5 \times ULN$
 - e) Albumin < 3.0 mg/ dL
 - f) INR $> 1.5 \times$ ULN (unless stable on anticoagulant regimen)
 - g) Total bilirubin $> 2.5 \times ULN$
- 7) Received solid organ or bone marrow transplant
- 8) Significant renal, cardiovascular, pulmonary, or neurological disease in the opinion of the investigator
- 9) Malignancy within 5 years prior to screening, with the exception of specific cancers that are cured by surgical resection (e.g. basal cell skin cancer, etc.). Subjects under evaluation for possible malignancy are not eligible.
- Currently receiving therapy with immunomodulators (e.g. corticosteroids), nephrotoxic agents, or agents capable of modifying renal excretion

- 11) Known hypersensitivity to study drugs, metabolites, or formulation excipients
- 12) Current alcohol or substance abuse judged by the investigator to potentially interfere with subject compliance

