Creatinine**	> 1.50 to 2.00 mg/dL	> 2.00 to 3.00 mg/dL	> 3.00 to 6.00 mg/dL	> 6.00 mg/dL	
	$>$ 133 to 177 μ mol/L	> 177 to 265 $\mu mol/L$	> 265 to 530 μmol/L	$> 530 \ \mu mol/L$	
Bicarbonate	16.0 mEq/L to < LLN	11.0 to < 16.0 mEq/L	8.0 to < 11.0 mEq/L	< 8.0 mEq/L	
Adult and Pediatric ≥ 4 Years	16.0 mmol/L to < LLN	11.0 to < 16.0 mmol/L	8.0 to < 11.0 mmol/L	< 8.0 mmol/L	
Pediatric < 4 Years	NA	11.0 mEq/Lto <lln< td="">8.0 to < 11.0 mEq/L	< 8.0 mEq/L	</lln<>	8.0 to < 11.0 mEq/L	< 8.0 mEq/L	
		11.0 mmol/L to <lln< td="">8.0 to < 11.0 mmol/L	< 8.0 mmol/L	</lln<>	8.0 to < 11.0 mmol/L	< 8.0 mmol/L	
Triglycerides	NA	500 to 750 mg/dL	> 750 to 1200 mg/dL	> 1200 mg/dL	
(Fasting)		5.64–8.47 mmol/L	> 8.47–13.55 mmol/L	> 13.55 mmol/L	
LDL (Fasting)	130 to 160 mg/dL	>160 to 190 mg/dL	> 190 mg/dL	NA	
Adult	3.35 to 4.15 mmol/L	>4.15 to 4.92 mmol/L	>4.92 mmol/L		
LDL (Fasting)	110 to 130 mg/dL	>130 to 190 mg/dL	> 190 mg/dL	NA	
Pediatric >2 to <18 years	2.84 to 3.37 mmol/L	>3.37 to 4.92 mmol/L	>4.92 mmol/L		
Hypercholesterolemia	200 to 239 mg/dL	> 239 to 300 mg/dL	> 300 mg/dL	NA	
(Fasting)	5.16 to 6.19 mmol/L	> 6.19 to 7.77 mmol/L	> 7.77 mmol/L		
Pediatric < 18 Years	170 to 199 mg/dL	> 199 to 300 mg/dL	> 300 mg/dL	NA	
	4.39 to 5.15 mmol/L	> 5.15 to 7.77 mmol/L	> 7.77 mmol/L		
Creatine Kinase	$3.0 \text{ to} < 6.0 \times \text{ULN}$	6.0 to < 10.0 × ULN	10.0 to < 20.0 × ULN	≥ 20.0 × ULN	

Calcium should be corrected for albumin if albumin is < 4.0 g/dL

An overlap between the Grade 1 scale and the Lab's normal range for creatinine may result for Male subjects >70 yrs. Please follow the Gilead convention of grading any result within the LLN and ULN a 0.

ENZYMES				
	Grade 1	Grade 2	Grade 3	Grade 4
AST (SGOT)	1.25 to 2.50 × ULN	> 2.50 to 5.00 × ULN	> 5.00 to 10.00 × ULN	> 10.00 × ULN
ALT (SGPT)	1.25 to 2.50 × ULN	> 2.50 to 5.00 × ULN	> 5.00 to 10.00 × ULN	> 10.00 × ULN
GGT	1.25 to 2.50 × ULN	> 2.50 to 5.00 × ULN	> 5.00 to 10.00 × ULN	> 10.00 × ULN
Alkaline Phosphatase	1.25 to 2.50 × ULN	> 2.50 to 5.00 × ULN	> 5.00 to 10.00 × ULN	> 10.00 × ULN
Total Amylase	> 1.0 to 1.5 × ULN	> 1.5 to 2.0 × ULN	> 2.0 to 5.0 × ULN	> 5.0 × ULN
Pancreatic Amylase	> 1.0 to 1.5 × ULN	> 1.5 to 2.0 × ULN	> 2.0 to 5.0 × ULN	> 5.0 × ULN
Lipase	> 1.0 to 1.5 × ULN	> 1.5 to 3.0 × ULN	> 3.0 to 5.0 × ULN	> 5.0 × ULN
Albumin	-	2.0 to < LLN g/dL	< 2.0 g/dL	NA
Pediatrics <16 years		20 to < LLN g/L	< 20 g/L	
	3.0 g/dL to < LLN	2.0 to < 3.0 g/dL	< 2.0 g/dL	NA

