7.2.1.2. Calcium Corrected for Albumin

Calcium corrected for albumin will be calculated and summarized by-visit for subjects in the Safety Analysis Set from baseline to Week 96, and separately for subjects in the Open-Label Analysis Set from open-label baseline to Week 96. The following formula will be used when both serum calcium and albumin results for a given blood draw are available and serum albumin value is < 4.0 g/dL.

Calcium corrected for albumin (mg/dL) serum calcium (mg/dL) $+ 0.8 \times (4.0 \text{ albumin (g/dL)})$

When albumin value is ≥ 4.0 g/dL, the actual calcium results will be used. Toxicity grading for calcium will be applied based on the corrected values.

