7.5. Child-Pugh-Turcotte Score

The Child-Pugh-Turcotte (CPT) score is calculated as: the sum of the scores related to the 5 items in the table below (if any of the components are missing, the score is not calculated):

Measure	1 point	2 points	3 points
Total Bilirubin (mg/dL)	< 2	2 - 3	> 3
Serum Albumin (g/dL)	> 3.5	2.8 - 3.5	< 2.8
INR	< 1.7	1.7 - 2.3	> 2.3
Ascites	None	Slight/Moderate (medically controlled)	Severe (medically uncontrolled)
Hepatic Encephalopathy	None	Slight/Moderate (medically controlled)	Severe (medically uncontrolled)

For summary purposes, the score will be further classified into classes: Class A (5-6 points), Class B (7-9 points), and Class C (10-15 points). The number and proportion of subjects in each class of CPT score will be summarized in a shift table with baseline, Week 48, and Week 96 CPT class based on subjects in the Safety Analysis Set during the entire study treatment period. The distribution of the CPT class at these visits will be compared between the 2 treatment groups adjusting for baseline class using rank ANCOVA {LaVange 2008}.

The summaries described above will be repeated for subjects in the Open-Label Safety Analysis Set from open-label baseline to Week 96, using open-label baseline in place of baseline, and no statistical comparisons will be performed.

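### Exclusion 6e sets its albumin limit in mg/dL while every other albumin cut-off is in g/dL or g/L, so taken alone it has no practical excluding effect

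*Protocol*

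**What the plan says.** Protocol Section 4.3, exclusion 6, lists haematological and biochemical abnormalities that bar entry. Item 6e is "Albumin < 3.0 mg/dL". The synopsis has the same item as "Albumin < 3.0 mg/ dL", which differs only by a space.

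Everywhere else, albumin is on a different scale:

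- Protocol Appendix 4, albumin at age 16 and over: Grade 1 is "3.0 g/dL to < LLN", Grade 2 is "2.0 to < 3.0 g/dL" and Grade 3 is below 2.0 g/dL. The same row is restated in g/L.
- Protocol Appendix 4, note under the chemistry table: "Calcium should be corrected for albumin if albumin is < 4.0 g/dL".
- SAP Section 7.2.1.2: the calcium correction applies when "serum albumin value is < 4.0 g/dL".
- SAP Section 7.5: the Child-Pugh-Turcotte table scores albumin in g/dL, with cut-offs at 3.5 and 2.8.

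The SAP's eligibility summary (Section 1.2.3) mentions abnormal laboratory parameters but gives no albumin value, so it does not settle the unit.

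**The concern.** Item 6e is a numeric entry limit that sites are meant to apply, not background text. If its unit is wrong by a factor of 1000, the written rule and the rule that sites actually followed may differ, and the documents give no way to tell which was used.

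Two features of the trial give this some weight. First, Protocol Section 3.1 admits subjects with compensated cirrhosis. Albumin, like INR and bilirubin, is both a numeric limit in exclusion 6 and a component of the Child-Pugh score. Second, eligibility is recorded on a dedicated eCRF (Protocol Section 9.1.6), and SAP Section 4.3 plans a listing of subjects who missed an eligibility criterion. On the literal text, a subject with low albumin would not appear in that listing because of 6e. On a g/dL reading, the same subject might.

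**Working it through.** The plan derives nothing from this threshold, so there is no computed figure to reproduce. The check is a unit conversion, followed by a comparison with every other albumin cut-off.

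**Inputs**

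- Written threshold: 3.0 mg/dL (Protocol synopsis and Section 4.3, item 6e).
- Appendix 4 cut-offs: 2.0 and 3.0 g/dL.
- SAP Section 7.5 cut-offs: 2.8 and 3.5 g/dL.
- Calcium-correction cut-off: 4.0 g/dL (Protocol Appendix 4; SAP Section 7.2.1.2).

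**Conversion**

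1 g/dL = 1000 mg/dL, so 3.0 mg/dL ÷ 1000 = 0.003 g/dL = 0.03 g/L.

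**Comparison** (ratio = cut-off ÷ 0.003 g/dL)

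| Cut-off | In mg/dL | Ratio to 6e as written |
|---|---|---|
| 2.0 g/dL (Grade 3 boundary) | 2000 | 667 |
| 2.8 g/dL (Child-Pugh, 3 points below this) | 2800 | 933 |
| 3.0 g/dL (Grade 1/Grade 2 boundary) | 3000 | 1000 |
| 3.5 g/dL (Child-Pugh, 1 point above this) | 3500 | 1167 |
| 4.0 g/dL (calcium correction) | 4000 | 1333 |

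A subject well inside the worst albumin grade would still be far above 0.003 g/dL and would not meet 6e. If the numeral 3.0 were read in g/dL, it would fall exactly on the Grade 1/Grade 2 boundary of Appendix 4. That makes a unit slip the likely explanation, but it does not prove what was intended.

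**Is anything statistical affected?** No. The non-inferiority sample size uses a 2.4% rate in both arms, a 4% margin and 230 per arm:

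- standard error = √(2 × 0.024 × 0.976 ÷ 230) = 0.01427
- power = Φ(0.04 ÷ 0.01427 − 1.96) = Φ(0.843) = 80.0%

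This matches the stated 80%, and albumin does not enter the calculation.

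**The case against.** The best reply is that this is a self-evident typing error with little consequence. Most of that reply stands.

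- **Other criteria remain.** A reader might infer that everyone with Grade 2 or Grade 3 albumin was eligible, or that no enrolment with low albumin could be called a deviation. The documents do not support either. The heading of exclusion 6 is open-ended, so its listed items are examples. Exclusions 5 (decompensation), 6f (INR), 6g (bilirubin) and 13 (investigator's opinion) also apply. Protocol Section 3.1 limits eligible cirrhosis to subjects with no laboratory or clinical evidence of decompensation. The accurate statement is that such subjects are not excluded by 6e alone.
- **Literal use is not shown.** The documents describe no automated albumin check. Staff complete the Eligibility Criteria eCRF once the eligibility data are in, and many sites probably read the unit as g/dL.
- **Appearing twice adds no weight.** The two exclusion lists are nearly identical, so one slip copied across would produce the same pattern. The repetition makes a PDF-reading error unlikely, but it does not make the error more consequential.
- **It comes late.** The SAP, signed in March 2020, records in Section 2.2 that the Week 48 analysis had been done. A correction cannot change who was enrolled.

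The reply does not remove the contradiction. An entry limit is wrong as written in both places where it appears, and nothing elsewhere repairs it. If sites did read g/dL, they applied a rule that the protocol does not state.

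**Conclusion.** The point holds for item 6e taken alone. As written, its threshold is 0.003 g/dL, and the lowest albumin cut-off used anywhere in the documents is about 667 times as large. It therefore has no practical excluding effect.

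The conversion is exact. The practical conclusion rests on one inference: the documents give no physiological minimum for albumin, but it is safe to assume that no screening value falls hundreds of times below their worst grade.

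The effect on the enrolled population is unknown and may be nil. It depends on which unit sites used and on how many candidates with low albumin were caught by other criteria, and neither is documented. For context only, Protocol Section 1.2.3 reports graded albumin decreases in 8 TAF subjects (0.9%) and 8 TDF subjects (1.9%) in the two earlier Phase 3 studies. Those are on-study abnormalities of any grade in a different population, so they do not estimate how many candidates here would fall below any given limit.

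No endpoint, analysis set, test or sample-size figure depends on the threshold. This is a definite error in an operative criterion. It should be corrected, but it does not threaten the trial's conclusions.

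**What to change.** 1. Reconcile the unit of item 6e in the synopsis and Section 4.3 with the g/dL scale of Appendix 4 and SAP Sections 7.2.1.2 and 7.5. The sponsor should confirm the intended threshold, because the documents alone do not establish that only the unit is wrong.
2. Confirm which unit was applied when the Eligibility Criteria eCRF was completed (Protocol Section 9.1.6).
3. Confirm that the SAP Section 4.3 listing of unmet eligibility criteria used the same unit, and record this in the clinical study report.

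Step 1 is a unit correction in two places, by administrative letter or with any further amendment. Steps 2 and 3 need a check against the eCRF instructions and the screening albumin values already collected. No re-analysis is needed. Because enrolment was complete by the time of the SAP, the gain is a clear record of how the criterion was applied.

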5. INVESTIGATIONAL MEDICINAL PRODUCTS

5.1. Randomization, Blinding and Treatment Codes

A centralized randomization procedure via an Interactive Voice/Web Response System (IVRS/IWRS) will be used for this study, whereby study treatment will be assigned to subjects according to the randomization schedule. A unique subject number will be provided during randomization. Eligible subjects (n = 300) will be randomized 1:1 to receive either blinded TAF 25 mg and TDF matched placebo (n = 150) or TDF 300 mg and TAF matched placebo (n = 150) for 48 weeks. Subjects will be stratified by HBeAg status (HBeAg-negative [and anti-HBe positive] vs. HBeAg-positive) and age (> 50 years vs. < 50 years). At Week 48, all subjects will be switched to open-label TAF 25 mg QD for an additional 48 weeks (through Week 96/ED). For the entire duration of the study, subjects and investigators will remain blinded to the initial treatment regimen to which the subjects were randomized.

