- 13) Any other clinical condition or prior therapy that, in the opinion of the Investigator, would make the subject unsuitable for the study or unable to comply with dosing requirements.
- 14) Use of investigational agents within 3 months of Screening, unless allowed by the Sponsor
- 15) Use of any prohibited medications as described in Section 5.4. Subjects on prohibited medications, who are otherwise eligible, will need a wash out period of at least 30 days prior to the Baseline visit.

Study Procedures/ Frequency:

- Screening Visit
- Treatment Period Visits: Baseline/Day 1, Weeks 4, 8, 12, 24, 36 and 48, and open label Weeks 60, 72, and 96/Early Discontinuation (ED)
- Subjects who permanently discontinue study drug (either prematurely or at the end of study [Week 96]) for reasons other than HBsAg loss with confirmed seroconversion to anti-HBs will be followed every 4 weeks for 24 weeks off treatment or until initiation of appropriate, alternative, HBV therapy, whichever occurs first. Use of appropriate, alternative HBV therapy is strongly encouraged.
- Review of concomitant medications and assessment for adverse events and vital signs, and weight measurement will be conducted at all study visits.
- Laboratory analyses (serum chemistry, hematology, eGFR_{CG}, urinalysis, plasma HBV DNA levels, pregnancy testing [for females of childbearing potential]) will be conducted at all study visits.

Screening Visit assessments include:

[figure not shown]
- Complete physical examination with height, body weight, and vital signs and medical history (including HBV disease and treatment history)
- INR and Alpha-fetoprotein (AFP); an AFP > 50 ng/mL at Screening must have an appropriate evaluation (e.g.., CT scan) in order to rule out HCC prior to being permitted to enter the study.

- Plasma HBV DNA levels (must be < 20 IU/mL at time of Screening to be eligible)
- HBV serology (qualitative HBsAg, and qualitative HBeAg; HBeAb and HBsAb reflex testing will be performed as needed) and quantitative HBsAg
- HCV, HDV and HIV testing
- Urinalysis and urine drug screen
- Baseline DXA scans of the hip and spine can be conducted anytime during the Screening period, but should be conducted at least 14 days prior to the Baseline visit to ensure results are received prior to the first dose of study drug
- ECG

Baseline and On-treatment assessments include:

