4. SUBJECT POPULATION

4.1. Number of Subjects and Subject Selection

Approximately 460 subjects (with approximately 50% of subjects being \geq 50 years old) will be randomized in a 1:1 ratio (A:B) to receive either TAF 25 mg QD and matched placebo of TDF 300 mg QD or Gilead-provided TDF 300 mg QD and matched placebo of TAF 25 mg QD.

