5.3. Dosage and Administration of Tenofovir Alafenamide (TAF) and TDF

Subjects will be randomly assigned (1:1) to receive one of the following treatments in a blinded fashion:

- Treatment Arm A: approximately 230 subjects administered TAF 25 mg QD and matched placebo of Tenofovir DF (TDF) 300 mg QD
- **Treatment Arm B:** approximately 230 subjects administered Gilead-provided TDF 300 mg QD and matched placebo of TAF 25 mg QD

It is preferred that subjects take their study drug according to a morning dosing schedule; however, evening dosing is allowable.

All study drugs should be taken at approximately the same time each day with or without food. Subjects taking TDF 300 mg QD with food prior to randomization should continue to take study drug with food; subjects taking TDF 300 mg QD without food prior to randomization should continue to take study drug without food during the study period.

Study drug should be administered after assessing adverse events and concomitant medication(s).

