6.1. Subject Enrollment and Treatment Assignment

It is the responsibility of the investigator to ensure that subjects are eligible to participate in the study prior to enrollment. Once consent has been obtained, all screening tests and procedures have been completed, and study eligibility has been confirmed, subjects will be randomized within 45 days using an IVRS/IWRS. Subjects will receive study drugs within their assigned treatment group as described in Section 3.1.

Candidates who fail to meet eligibility criteria by screening evaluations may be re-screened once after the initial screen if there is a reasonable expectation that the candidate will be eligible after repeat screening.

Retesting of an exclusionary laboratory value during the Screening period is permitted only if in the Principal Investigator's opinion, the retest value will be within accepted parameters; if the initial value was deemed to be inaccurate, inconsistent with the subject's previous result(s); in error (e.g. mishandled sample); or due to an extenuating circumstance.

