8.9. Sample Size

With respect to the primary efficacy endpoint of proportion of suppressed subjects with HBV DNA \geq 20 IU/mL (current assay LLOQ), as determined by the modified US FDA-defined snapshot algorithm, at Week 48, when the sample sizes are 230 (TAF 25 mg arm) and 230 (TDF 300 mg arm), a two-group, large-sample normal approximation test of proportions with a one-sided 0.025 significance level will have 80% power to establish non-inferiority of TAF to TDF. It is assumed that both treatment arms will have subjects who have HBV DNA \geq 20 IU/mL (as defined by the modified US FDA-defined snapshot algorithm) at a rate of 2.4% at Week 48 (based on the rates of suppressed subjects having HBV DNA \geq 29 IU/mL [the LLOQ of assay during those studies] after 48 weeks of treatment from the combined data of studies GS-US-174-0102 and GS-US-174-0103 with the ratio of HBeAg- to HBeAg+ subjects assumed to be 2:1), with a non-inferiority margin of 4%.

The proposed sample size (n = 230 for the TAF 25 mg arm, n = 230 for the TDF 300 mg arm) also provides > 99% power to detect a 1.81% difference in the percentage change from baseline in hip BMD at Week 48 (assuming a 1.47% [SD 2.71%] change from baseline in TAF 25 mg arm and -0.34% [SD 2.83%] change from baseline in the TDF 300 mg arm, with a two-sided $\alpha = 0.05$); a > 99% power to detect a 2.00% difference in the percentage change from baseline in spine BMD at Week 48 (assuming a 1.56% [SD 3.84%] change from baseline in the TAF 25 mg arm and -0.44% [SD 4.14%] change in the TDF 300 mg arm, with a two-sided $\alpha = 0.05$); a 97% power to detect a 4.9 mL/min difference in the change from baseline in eGFR_{CG} at Week 48 (assuming a 1.3 mL/min [SD 13.2] change from baseline in the TAF 25 mg arm and -3.6 mL/min [SD 13.0] change from baseline in the TDF 300 mg arm, with a two-sided $\alpha = 0.05$). These assumptions were derived from an HIV switch study (GS-US-292-0109) due to the unavailability of switch data from TAF HBV studies.

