1.2.2. Treatment Groups and Randomization

At randomization, subjects will be stratified by screening HBeAg status (HBeAg-negative vs. HBeAg-positive) and age (≥ 50 or < 50 years).

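### Protocol 5.1 gives 300 subjects (150 per arm) and an anti-HBe condition on the HBeAg-negative stratum; the rest of the plan gives about 460 (230 per arm) and no such condition

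*Protocol*

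**What the plan says.** **Sample size.** Protocol 5.1 reads "Eligible subjects (n = 300) will be randomized 1:1 to receive either blinded TAF 25 mg and TDF matched placebo (n = 150" and gives 150 for the TDF arm too. Protocol 4.1 instead opens with "Approximately 460 subjects (with approximately 50% of subjects being" at least 50 years old. Protocol 5.3 describes Arm A as "approximately 230 subjects administered TAF 25 mg QD and matched placebo of Tenofovir DF (TDF) 300 mg QD" and gives the same number for Arm B. Protocol 8.9 attaches its power statement to 230 per arm: "when the sample sizes are 230 (TAF 25 mg arm) and 230 (TDF 300 mg arm". The synopsis, Protocol 3.1 and SAP 1.2.1 and 1.3 agree with about 460, or 230 per arm.

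**Strata.** Protocol 5.1 says: "Subjects will be stratified by HBeAg status (HBeAg-negative [and anti-HBe positive] vs. HBeAg-positive", together with age. SAP 1.2.2 says: "subjects will be stratified by screening HBeAg status (HBeAg-negative vs. HBeAg-positive) and age". The synopsis, Protocol 3.1 and 8.6.1, and SAP 3.3 and 6.2.2 also use HBeAg status and age without reference to anti-HBe.

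**Related text.** On antibody testing, the synopsis and the footnotes to the study procedures table say "HBeAb and HBsAb reflex testing will be performed as needed". Protocol 6.1 sends the reader elsewhere for the treatment groups: "Subjects will receive study drugs within their assigned treatment group as described in Section 3.1". SAP 3.3 reclassifies the HBeAg and age strata from baseline values for analysis. SAP 5.1 lists HBeAg-negative/HBeAb-negative as a baseline category. SAP 4.1 places the randomisation schedule in an appendix to the clinical study report.

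**The concern.** Section 5.1 describes the centralised IVRS/IWRS procedure and the randomisation schedule, so it is where a reader would look to learn how many subjects were to be randomised and on which strata. On both points it disagrees with every other section that states them.

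A trial of 150 per arm would not have the power that Protocol 8.9 claims. The stratum wording raises a separate question. If the bracket is a condition, the two HBeAg levels are not exhaustive, because a subject negative for both HBeAg and anti-HBe fits neither. The eligibility criteria do not exclude such a subject. The documents also do not say what triggers the anti-HBe reflex test, so they do not guarantee a result at randomisation.

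**Working it through.** **Inputs from Protocol 8.9 (repeated in SAP 1.3).** Failure rate 2.4% in both arms, margin 4%, one-sided alpha 0.025, 80% power, 230 per arm. For eGFR: difference 4.9 mL/min, SDs 13.2 and 13.0, two-sided alpha 0.05, 97% power. Neither document prints a power formula. I used the standard unpooled normal approximation, which fits the method the protocol names. No dropout inflation is given, so none is applied.

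**1. Reproduce the plan's figure.**

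n per arm = (1.96 + 0.8416)² × 2 × 0.024 × 0.976 / 0.04² = 229.8, which rounds up to 230.

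Power = Φ(0.04 / √(2 × 0.024 × 0.976 / n) − 1.96)

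- n = 230: Φ(0.04 / 0.01427 − 1.96) = 80.0%, as stated.
- n = 150: Φ(0.04 / 0.01767 − 1.96) = 61.9%.

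**2. Allow for few events.** Expected failures per arm are 0.024 × 230 = 5.5 and 0.024 × 150 = 3.6, so the normal approximation is rough. I therefore summed exact binomial probabilities over all outcome pairs for which the upper limit of the unstratified 95% normal-approximation interval is below 4%. The planned interval is stratified, so this too is approximate.

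**3. eGFR.** Common SD = √((13.2² + 13.0²) / 2) = 13.1. Protocol 8.7.1 plans a Wilcoxon test. I assumed normal data and relative efficiency 3/π = 0.955, so effective n = 0.955 × n.

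| Quantity | 230 per arm | 150 per arm |
|---|---|---|
| Total subjects | 460 | 300 |
| Primary power, normal approximation | 80.0% (stated 80%) | 61.9% |
| Primary power, exact evaluation | 79.0% | 63.0% |
| eGFR power, t-test | 97.9% | 89.8% |
| eGFR power, Wilcoxon | 97.4% (stated 97%) | 88.4% |

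The shortfall in subjects is (460 − 300) / 460 = 35%. Hip and spine BMD power stays above 99% at 150 per arm. The stated power figures fit 230 and not 150, so 300/150 is the outlier.

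**4. Strata side by side.**

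| Subject at screening | Protocol 5.1, read literally | Synopsis, Protocol 3.1, SAP 1.2.2 and 3.3 |
|---|---|---|
| HBeAg positive | HBeAg-positive | HBeAg-positive |
| HBeAg negative, anti-HBe positive | HBeAg-negative | HBeAg-negative |
| HBeAg negative, anti-HBe negative | none | HBeAg-negative |

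The last row is not hypothetical for the plan: SAP 5.1 provides a category for it. The documents do not say how many such subjects there are, so this part cannot be sized.

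**The case against.** The strongest reply is that this is leftover text with no consequence. One sentence stands against many that agree, including the sections that set the size (Protocol 4.1 and 8.9, SAP 1.3). Protocol 6.1 points to Section 3.1 for the treatment groups. No endpoint, threshold or power statement uses 300, so the figures at 150 per arm are counterfactual. This stands, and it limits the finding to a documentation error.

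The bracket can also be read as describing the usual HBeAg-negative profile, since the sentence names the factor as HBeAg status. SAP 5.1 supports that reading: its table covers the Open-Label Safety Analysis Set, whose members were all randomised, so it assumes that HBeAg-negative, anti-HBe-negative subjects could be randomised. For analysis, SAP 3.3 and 6.2.2 settle the matter with HBeAg status and age. This makes the stratum point the weaker half. It does not remove it, because Section 5.1 does not call the bracket descriptive and reclassifying strata for analysis does not show which strata the system used.

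Finally, the SAP was signed in March 2020, after the Week 48 analysis, so randomisation was over and editing Section 5.1 changes no conduct. That is true. The remaining value lies in an accurate record. The rest of Section 5.1 (central system, 1:1 allocation, 48 blinded weeks, open-label switch) matches the other sections and is not in question.

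**Conclusion.** The inconsistency is real on both counts. The sample size in Protocol 5.1 is wrong as written: 300 against about 460, or 35% fewer. The plan's own assumptions confirm that 230 per arm is the intended number, and the stated 80% power is correct for it. The power loss to about 62–63% for the primary test, and to about 88% for eGFR under the Wilcoxon assumptions, would apply only if 150 per arm had been followed.

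The anti-HBe bracket conflicts with every other statement of the HBeAg strata and, if literal, leaves one group of eligible subjects unassigned. It may be only descriptive. The documents do not show that either the 300 or the bracket was used, and neither changes a planned analysis. The point deserves correction because of where it sits, but it does not call the result into question.

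**What to change.** In Protocol 5.1, replace 300 and 150/150 with approximately 460 and 230/230. Delete the anti-HBe bracket so that the HBeAg levels match Protocol 3.1 and the SAP.

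Check the IVRS/IWRS specification to confirm that HBeAg status was used without anti-HBe. State the stratum definitions actually used beside the randomisation schedule that SAP 4.1 already places in the study report appendix. If the protocol will not be amended again, a short note in the report can carry both corrections.

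The age boundary is printed as strictly above 50 in Protocol 3.1 and 5.1 and as 50 or above elsewhere. That may be a text-extraction error and is not part of this finding.

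The cost is a wording correction and one check of the system's strata. No patients are added, because about 460 is already the plan, and no analysis changes.
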